#### *4.2.2. Discontinuation of Study Centers*

Study center participation may be discontinued by the sponsor, the investigator, or the Institutional Ethics Committee/Institutional Research Board (IEC/IRB) for any reason (e.g., legal, regulatory, non-performance, or GCP compliance issues).

#### *4.2.3. Discontinuation of the Study*

This clinical study may be prematurely terminated, patient enrollment may be suspended, or IMP administration may be halted due to a decision by a regulatory authority, a change in opinion of the IEC/IRB, safety concerns, or at the discretion of the sponsor. The sponsor retains the right to discontinue development of the IMP at any time. If the study is prematurely terminated, the sponsor will promptly notify the investigator. The investigator may also terminate the study at his/her study center for reasonable cause, if written notice is provided to the sponsor in advance of the intended termination.

The occurrence of any of the following in any patient in any part of this study will prompt an immediate suspension of patient enrollment and IMP administration:

- Death in any patient which the investigator deems to be possibly related to administration of the IMP.
- Any other event which is considered sufficiently serious by the investigator or the medical representative of the sponsor to warrant immediate safety review.

A cumulative review of safety data and the AE in question must be promptly conducted by the SAC to determine whether to resume the study, modify the protocol, or permanently terminate the study. If the SAC recommends permanent termination of the study, the sponsor will provide instructions to the investigators.

## 5. TREATMENT

### 5.1. Rationale for Selection of Dose

Preclinical Good Laboratory Practice toxicology studies identified CCI [REDACTED] as the highest non-severely toxic dose (HNSTD) in dogs. The safe starting dose was calculated as one-sixth the HNSTD adjusted for body surface area, CCI [REDACTED]. Consequently, the starting dose for Phase I was chosen to be 25 mg BID (50 mg daily). Escalation beyond this dose will be guided by safety, exposure, and PD data (as available) until an MTD is established or the highest planned dose of 800 mg BID is reached.

A PK/PD model for efficacy in a murine xenograft tumor model supported *in vitro* findings that AK-01 concentrations above IC90 elicit cell death and tumor growth inhibition. Thus, the target for efficacy used to project the human efficacious dose range was 90% inhibition of pAurA maintained over two-thirds of the dosing interval (i.e., 8 hours for twice daily dosing). Twice daily dosing is suggested to maintain adequate time on target. CCI [REDACTED]

The 25 mg BID has been chosen by the SAC and sponsor as the dose of Phase II. Dose selection was based on the MTD, AurA and AurB target engagement, and PK from Phase I (see [Section 3.1.3](#)).

Further details on the rationale for dose selection may be found in the Investigator's Brochure.

### 5.2. Investigational Medicinal Product

AK-01 drug product will be supplied by the sponsor as capsules containing 25 mg AK-01 drug substance and no inactive ingredients. AK-01 IMP consists of bottles containing 16 capsules of 25 mg, which will be supplied to the designated pharmacy of each study center.

IMP will be supplied by the sponsor. The sponsor is responsible for ensuring that IMP is manufactured according to current Good Manufacturing Practice regulations and requirements, and that labeling meets any local regulations.

All supplied IMP will be for investigational use only and will only be dispensed to patients enrolled in this study. The investigator or designee will ensure that all IMP is maintained in a restricted area according to regulatory and study center requirements. IMP will be stored at room temperature (15°C -30°C) at the study center, and patients will be instructed to store IMP dispensed for home administration at room temperature.

Preparation, dispensing, and storage of IMP will follow routine pharmacy procedures. Handling should be limited to individuals involved in dispensing and administering IMP (including the patients for home administration).

Patients will be dispensed IMP as follows: Days 1, 8, and 15 for Cycle 1 of Phase I, Day 1 for Cycles ≥2 of Phase I, and Day 1 for all cycles of Phase II. AK-01 may be dispensed up to 2 days prior to each scheduled dispensing day to facilitate patient scheduling.

### 5.2.1. Investigational Medicinal Product Administration

Doses of AK-01 taken at the study center will be administered by trained study personnel and will be recorded. Any dose reductions or dose interruptions will be recorded with the associated reasons. Patients will be given instructions for home dosing. Confirmation of home administration will be based on measurements of treatment compliance (see [Section 8.1.5](#)).

AK-01 should be taken orally according to the assigned dosing schedule and the investigator's instructions. Patients will take AK-01 twice a day approximately 12 hours apart. Patients will be encouraged to fast for 1 hour prior and 1 hour following each dose.

Doses of AK-01 should be taken at approximately the same time each day during the dosing period. If a dose of AK-01 is missed, it should be reported as such and should not be combined with a dose on another day. If a dose of AK-01 is vomited, it should be reported as such and should not be repeated.

### 5.2.2. Dose and Regimen

AK-01 will be administered twice daily, every day of a 21-day cycle. Patients will be dosed continuously: there will be no dosing holiday between cycles.

In Phase I, the dose of AK-01 will be between 25-75 mg BID per day (see [Table 3](#)). Patients in the first cohort of Phase I will receive 25 mg BID AK-01. Following a review of safety and other relevant data from this cohort, the SAC will decide on the dose for the subsequent cohort based on [Table 3](#). Following DLT or completion of Cycle 1, dosing for a given patient will be based on individual safety and tolerability.

For Phase II, the sponsor and SAC has established the dose of AK-01 as 25mg BID.

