### **1.3. Data from Ongoing Phase I Part of the Study**

A total of 12 patients have been dosed in the ongoing Phase I part of the study since June 2017 with doses of AK01 of up to 75 mg BID. Dose- limiting- toxicities (DLTs) were noted at both 75 mg and 50 mg dose levels. The 25 mg twice a day (BID) dose has been chosen as the dose for Phase II.

Based on safety analysis of the ongoing Phase I part of the study, the following are considered as potential adverse events (AEs): bone marrow toxicity including neutropenia and thrombocytopenia; gastrointestinal toxicity including mucositis and diarrhea; and corneal deposition with blurry vision and double vision. Appropriate follow up and rapid therapy for any of these events will be undertaken.

Additional information on the reported AEs is available in the investigator's brochure (IB).

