the event recurs at 25 mg QD, the patient will be  
withdrawn.

**The sponsor must be notified of dose reductions. Given the P2D of 25mg BID, the only dose reduction allowed will be a reduction in dosing frequency from 25mg BID to 25mg QD.**

Following dose reduction and recovery, re-escalation of a patient's dose will be at the discretion of the sponsor in discussion with the investigator. Re-escalation must not exceed the dose at which toxicity was experienced.

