**Table 3. AK-01 Dosing**

Dose Level	Capsules Administered	Total Daily Dose
25 mg QD	1 × 25 mg	25 mg
25 mg BID	1 × 25 mg (morning) 1 × 25 mg (evening)	50 mg

The dose of AK-01 may be reduced and/or interrupted for toxicity as described in [Section 3.3.2](#).

After monitoring visits, at study completion and after the close-out visit, unused AK-01 and dispensed medication bottles returned by patients will be sent to the sponsor or designee, unless the sponsor and study centers have agreed to destruction of AK-01 by the study center, as allowed by local law.

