#### 5.1.2. Phase II

Phase II will evaluate the preliminary efficacy of AK-01 in up to 4 cohorts; initially in patients with locally advanced or metastatic small-cell lung cancer (SCLC) and breast cancer (BC), and subsequently, at sponsor's discretion, in patients with TNBC, SCC-HN, and OT. Up to 30 patients may be enrolled in each cohort, giving an estimated total of 120 patients. Since AK-01 is an experimental treatment, patients will need to have failed standard of care therapies (i.e., platinum-

based therapy for SCLC; hormone therapy and a CDK4/6 inhibitor for BC; relapsed/resistant TNBC patients; standard therapy for HPV associated SCC-HN) before being enrolled in this trial.

All open cohorts in Phase II may begin enrollment concurrently and will be dosed at 25 mg BID. Dose increases will not be allowed in Phase II.

After Cycle 1, dosing of AK-01 may continue in 21-day cycles until disease progression if the patient is receiving benefit, and is experiencing no severe toxicity in the opinion of the investigator.

Dose modifications for toxicity for both phases are described in the Protocol, Section 3.3.2.

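### The Phase I dosing text contradicts itself: Section 5.2.2, Section 5.1 and Table 3 imply three different top doses, and the reduction rule in Section 3.3.2 does not fit patients on 50 or 75 mg BID

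*Protocol*

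**What the plan says.** Three places in the current protocol describe the Phase I dose range.

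- Section 5.2.2: "In Phase I, the dose of AK-01 will be between 25-75 mg BID per day", with a reference to Table 3. The first cohort receives 25 mg BID. After that, "the SAC will decide on the dose for the subsequent cohort based on" Table 3.
- Section 5.1: escalation beyond 25 mg BID continues "until an MTD is established or the highest planned dose of 800 mg BID is reached".
- "Table 3. AK-01 Dosing" has two rows, 25 mg QD (25 mg in total per day) and 25 mg BID (50 mg in total per day).

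Section 1.3 calls Phase I ongoing. It reports 12 patients dosed at up to 75 mg BID, with DLTs "noted at both 75 mg and 50 mg dose levels". SAP Section 7.2 names 25, 50 and 75 mg BID as Phase I cohort labels and leaves the list open.

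On toxicity, Protocol Sections 3.1.1 and 3.1.4 send Phase I patients to Section 3.3.2, and SAP Section 5.1.2 confirms the scope: "Dose modifications for toxicity for both phases are described in the Protocol, Section 3.3.2". The opening text of Section 3.3.2 and the rows of Table 1 provide for resuming at the same dose or at a lower dosing frequency, with no starting dose named. The paragraph below Table 1, which opens by referring to the Phase II dose (P2D) of 25 mg BID, then says "the only dose reduction allowed will be a reduction in dosing frequency from 25mg BID to 25mg QD". For recurrent Grade 3 non-hematologic toxicity and for hematologic toxicity, Table 1 withdraws the patient if the event recurs at 25 mg QD.

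**The concern.** Section 5.2.2 gives the SAC an instruction that its own table cannot serve: a next-cohort dose is to be taken from a list that ends at the starting dose. A site or SAC member who looks for the Phase I ceiling finds a different answer in each of three places.

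The toxicity rules appear to have been rewritten around 25 mg BID while still being cited for Phase I. A patient on 50 or 75 mg BID who needs a reduction meets a sentence that permits one step only, from a dose the patient is not taking, and a withdrawal trigger set at a level that a frequency reduction would not reach. These are the levels at which DLTs were noted. At stake is operative, safety-relevant dosing text that different sites could apply differently.

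**Working it through.** No sample size, power or error rate is involved. The check is daily-dose arithmetic followed by a side-by-side reading.

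**Step 1. Reproduce Table 3.** Daily dose = mg per intake × intakes per day.
- 25 mg QD: 25 × 1 = 25 mg/day, as stated.
- 25 mg BID: 25 × 2 = 50 mg/day, as stated.

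**Step 2. Compare the three top doses.**

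| Source | Top Phase I dose | Daily total |
|---|---|---|
| Table 3 | 25 mg BID | 25 × 2 = 50 mg |
| Section 5.2.2 | 75 mg BID | 75 × 2 = 150 mg |
| Section 5.1 | 800 mg BID | 800 × 2 = 1600 mg |

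The two ceilings in the text differ by 800/75 = 10.7-fold. The Section 5.2.2 range is 50 to 150 mg/day, and Table 3 covers only its lowest point. Of the three dose levels named in SAP Section 7.2, two (50 and 75 mg BID) have no row in Table 3. The table holds no level above the starting dose.

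**Step 3. Is Phase I still live on paper?** Section 1.3 calls it ongoing, with 12 dosed; the synopsis allows up to 30. Section 3.1.3 keeps the escalation rules, Section 3.1.4 still allows within-patient escalation up to the MTD, and Section 6.5.5 still has the SAC meet before each new cohort opens. Nothing states that escalation is closed.

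**Step 4. Apply Section 3.3.2 to a patient on 50 or 75 mg BID.**
- Under the sentence below Table 1, read literally, the patient is not on 25 mg BID, so the one permitted step is unavailable.
- Under the Section 3.3.2 introduction and the Table 1 rows, a lower frequency is allowed. Halving the frequency at an unchanged capsule dose gives 50 mg QD (50 mg/day) or 75 mg QD (75 mg/day). Neither is 25 mg QD, so the recurrence trigger is not met at that step, and the text does not say what follows. 75 mg/day also matches no row of Table 3.

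The two readings give different answers, and neither leads to the 25 mg QD trigger.

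The dose rows struck out in Appendix 12 are superseded text and play no part in this check.

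**The case against.** A reader might infer more than the documents support on four counts.

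**That patients on 50 or 75 mg BID have no permitted reduction.** The restrictive sentence is introduced by reference to the P2D and reads most naturally as addressed to patients at that dose. The rest of Section 3.3.2 allows a lower frequency from any dose. Section 5.2.2 bases dosing after a DLT or Cycle 1 on individual safety and tolerability, and Section 3.1.1 requires interruption after a DLT with sponsor consultation. Several exits do not depend on dose: no recovery within 21 days, Grade 4 non-hematologic toxicity, Grade 4 QTcF prolongation, a third Grade 3 QTcF event, and unacceptable toxicity under Section 4.2.1. This objection stands. It reduces the finding from an absent rule to a contradictory or undefined one.

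**That 800 mg BID is a live competing ceiling.** Section 5.1 makes it an alternative to establishing an MTD, and the same section says the Phase II dose was selected on the basis of the MTD. The figure looks like leftover text. Section 1.3 reports doses only up to 75 mg BID, and nothing routes a patient towards 800 mg. This also stands, but the number remains in current text and conflicts with Section 5.2.2.

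**That the SAC has no escalation levels anywhere.** Figure 1 could not be seen in the text available for this review. Its note says dosing may vary from the proposed doses, so the figure may list levels. Section 3.1.3 also refers to a separate document on communicating dose decisions. What is shown is narrower: Table 3, the source Section 5.2.2 names, has no higher level.

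**That the MTD data are compromised.** The MTD rests on Cycle 1 DLTs by cohort. SAP Section 8.1 keeps any patient with a DLT in the DLT set, and SAP Section 7.6 assigns each Phase I AE to the last dose given before onset, expressly allowing for dose changes. At most, AEs after a frequency reduction from 50 or 75 mg BID have no named cohort label in SAP Section 7.2, and that list is left open.

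**Conclusion.** The inconsistency is real and should be corrected. Sections 5.2.2 and 5.1 and Table 3 imply top doses of 150, 1600 and 50 mg/day, and the instruction to choose the next cohort's dose from Table 3 cannot be used for escalation. In Section 3.3.2, the reduction sentence and the 25 mg QD trigger do not fit a Phase I patient above 25 mg BID. For such a patient the rule is contradictory or undefined.

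The practical size is unknown. The documents do not say how many patients remain on 50 or 75 mg BID, and the number could be zero. The effect on further escalation may be small because the Phase II dose is already chosen. The conclusion assumes that Phase I is still open, as Section 1.3 says, and that Section 3.3.2 applies to it, as SAP Section 5.1.2 says. No effect on the MTD determination or on the Phase II efficacy analysis is claimed.

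**What to change.** Reconcile Protocol Sections 3.3.2 (including Table 1 and the paragraph below it), 5.1, 5.2.2 and Table 3 so that:

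1. Sections 5.1 and 5.2.2 state the same Phase I ceiling.
2. Either Table 3 agrees with the dose range that cites it, or the text states that escalation is closed and drops the instruction to select from Table 3.
3. Section 3.3.2 states which patients the sentence on the only allowed reduction and the 25 mg QD withdrawal trigger cover.

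What the ceiling, levels and reduction rules should be is for the sponsor and SAC to decide; no dose or rule is proposed here. The cost is protocol wording and possibly a few table rows, with no added patients or procedures.

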**Table 3. AK-01 Dosing**

Dose Level	Capsules Administered	Total Daily Dose
25 mg QD	1 × 25 mg	25 mg
25 mg BID	1 × 25 mg (morning) 1 × 25 mg (evening)	50 mg

The dose of AK-01 may be reduced and/or interrupted for toxicity as described in [Section 3.3.2](#).

After monitoring visits, at study completion and after the close-out visit, unused AK-01 and dispensed medication bottles returned by patients will be sent to the sponsor or designee, unless the sponsor and study centers have agreed to destruction of AK-01 by the study center, as allowed by local law.

### **5.3. Method of Assignment to Treatment**

This study will be open-label and will not involve a randomization schedule. In Phase I when a cohort requires an additional patient, the priority to enroll a patient will be given to each center consecutively.

In Phase II a patient's tumor type will determine their allocation to cohort. Study centers will enroll competitively as eligible patients become available. The patients will be allocated to IMP only after the registration form is signed by both the investigator and sponsor representative.

#### *5.3.1. Special Treatment Considerations*

Patients will attend scheduled clinic visits (see Appendix 1) and comply with study criteria under their control. Any deviation from the prescribed dose or regimen will be recorded.

#### *5.3.2. Evaluable Patients*

Any patient who withdraws from the study before receiving IMP may be replaced.

Any patient in Phase I who is discontinued from the study before completing Cycle 1 or who receives <38 doses of IMP in Cycle 1 will be deemed non-evaluable for DLT assessment at that dose level, unless the patient experiences a DLT. Additional patients may be enrolled to a cohort in Cycle 1 if a patient is withdrawn for reasons other than a DLT (e.g., disease progression, non-compliance, or personal reasons) to ensure that an appropriate number of patients will be evaluated.

Any patient withdrawn for toxicity in Cycle  $\geq 2$  of Phase I will not be replaced.

Any patient withdrawn for toxicity in Phase II prior to completion of Cycle 1 may be replaced.

Any patient who is not evaluable for PK, PD, or biomarkers may be replaced upon consultation with the investigator(s) and the sponsor to ensure collection of sufficient data for interpretation.

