### 3.6. Determination of Sample Size

In Phase I, the 3 + 3 design dose escalates cohorts of up to 9 patients until the MTD is identified. Up to 6 additional patients may be dosed to inform the selection of a P2D. A sample size of approximately 30 patients was considered sufficient to identify the MTD and is not powered on the basis of statistical hypothesis testing.

In Phase II, up to 30 patients for each tumor type will be administered IMP (up to 120 patients total). An observed ORR (proportion of partial or complete responders by RECIST) of  $\geq 20\%$  with

a durability of at least 4 months will be considered evidence of efficacy. With 15 patients in a cohort, there is approximately 60% power to reject the null hypothesis of the ORR being  $\leq 5\%$  when the true ORR is 20% using a one-sided exact test for a single proportion at a significance level of 0.05. The power for this statistical test for a single tumor type without any adjustment for multiplicity is provided in [Table 2](#) using various observed ORRs.

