**Table 2. Statistical Power of Observed Overall Response Rates**

True ORR	10%	15%	20%	25%	30%
N=15	18%	40%	60%	76%	87%
N=20	13%	35%	59%	78%	89%

Thus, whenever the true ORR is at least 20%, a sample size of 15 or 20 patients per tumor type provides approximately 60% power to reject the null hypothesis.

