## 8. PHARMACOKINETIC, PHARMACODYNAMIC, SAFETY, AND EFFICACY DATA ANALYSES

### 8.1. Data Analysis Plans

#### 8.1.1. General Considerations

A detailed statistical analysis plan (SAP) will be developed prior to study completion and database lock, which will describe the endpoints and analyses for the study. Any deviations from the statistical analyses planned in this protocol or the SAP will be described in the clinical study report.

The administration of IMP, dose interruptions, and dose modifications will be listed with the associated reasons. Concomitant medications will be listed by patient with reason for use, dose, route, and date of administration at a minimum, and time of administration if available. Major protocol deviations will be listed by patient and by study center.

Safety analyses will be performed on the Full Analysis Set (all patients who receive at least 1 dose of IMP, whether or not they complete all protocol requirements).

PK analyses will include all patients who receive at least 1 dose of IMP and have PK data that is sufficient and interpretable, as determined by the sponsor.

PD analyses for target engagement will include all patients who receive at least 1 cycle of IMP and from whom samples are collected of sufficient quantity and quality for evaluation. PD analyses for hematological changes will include all patients who receive at least 1 dose of IMP and have PD data that is sufficient and interpretable, as determined by the sponsor.

ORR will be assessed in the Full Analysis Set as well as in all patients evaluable for efficacy (all patients who complete at least 1 cycle of IMP with adequate compliance [as described in [Section 8.5.1](#)], and had a tumor assessment by RECIST v1.1 at baseline and at least once following receipt of IMP). Subsequent analyses of efficacy may be limited to patients evaluable for efficacy.

Analysis of tumor molecular profile will include all patients who complete at least 1 cycle of AK-01, and have blood and pre-treatment tumor samples of sufficient quality and quantity to permit evaluation using next-generation sequencing or other technology. Comparisons of efficacy in patients with specific molecular profiles will include all patients who are evaluable for both efficacy and molecular profile, as described above.

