#### *8.1.6. Efficacy Analysis*

The primary assessment of efficacy in Phase II will be based on the ORR, which will be compared to 5% using a test of a single proportion. RECIST v.1.1 criteria will be used to determine the effect of AK-01 on tumor burden. ORR, duration of objective response, best response on study, progression-free survival, overall survival, and disease control rate may be summarized with descriptive statistics. The rate of disease control (stable disease, partial response, or complete response assessed by RECIST v. 1.1 in 2 consecutive scans) may be summarized by tumor type, as appropriate. Descriptive statistics will be used to analyze all tabulated efficacy data. Progression-free survival (PFS) and OS curves may be estimated using Kaplan-Meier methods.

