## 9.6. Analyses of Efficacy

### 9.6.1. Phase II Primary Objective

The primary endpoint of phase II is ORR. The primary statistical hypotheses

$$H_0: \text{ORR} \leq 0.05$$

will be tested against an alternative

$$H_A: \text{ORR} > 0.05$$

by the means of a one-sided exact binomial test for a single proportion at a significance level of 0.05. See Section 9.3.1 for details on the statistical test. No multiple testing adjustment will be applied. The ORR will be presented with an exact one-sided 95% confidence interval (Clopper & Pearson). The analysis will be performed in the FAS as well as in Efficacy evaluable analysis set. That means, if the analysis set includes patients with missing baseline assessments, non-measurable disease at baseline (though this would be a protocol deviation) or no evaluable post-baseline

assessments, they will be counted in the denominator and not in the numerator. The ORR will be summarized and tested by cohort.

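### The Phase II ORR is tested in two analysis sets with neither named as decisive, and the plan does not say how patients replaced after dosing count, so the evaluable-set test need not hold 5% for treated patients

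*Protocol*

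**What the plan says.** Protocol section 5.3.2 has two replacement rules that reach dosed Phase II patients. One is for toxicity: "Any patient withdrawn for toxicity in Phase II prior to completion of Cycle 1 may be replaced". The other is for missing pharmacology data and limits neither phase nor reason: "Any patient who is not evaluable for PK, PD, or biomarkers may be replaced upon consultation with the investigator(s) and the sponsor". Section 8.1.1 sets the threshold for one kind of PD evaluability: "PD analyses for target engagement will include all patients who receive at least 1 cycle of IMP". Section 6.2.1 places the on-treatment biopsy at Cycle 2 Day 8.

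SAP section 8.1 defines the FAS as everyone who took at least one dose. The Efficacy Evaluable set requires a completed cycle, 80% to 120% compliance, a baseline assessment and at least one later one. For the primary ORR, SAP section 9.6.1 states: "The analysis will be performed in the FAS as well as in Efficacy evaluable analysis set". In whichever set is analysed, patients without an evaluable post-baseline assessment go into the denominator as non-responders. The hypothesis is tested "by the means of a one-sided exact binomial test for a single proportion at a significance level of 0.05", cohort by cohort, without multiplicity adjustment.

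On size, protocol section 3.6 says: "In Phase II, up to 30 patients for each tumor type will be administered IMP (up to 120 patients total"). Below Table 2 it adds: "Thus, whenever the true ORR is at least 20%, a sample size of 15 or 20 patients per tumor type provides approximately 60% power". Neither document says whether a replaced patient counts toward the 15 or 20, or which of the two ORR tests settles the primary question.

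**The concern.** A patient withdrawn for toxicity in Cycle 1 has been treated and has failed before the first response scan, which Appendix 1 places around the end of Cycle 2. That outcome belongs in the response rate of treated patients. The FAS keeps it. The Efficacy Evaluable set removes it, and replacement can bring that set back to its planned size with patients who got through Cycle 1. A test of 5% in that set asks about Cycle 1 completers, yet it is run at the same level as the FAS test and with equal standing.

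Two things are at stake. The evaluable-set test may exceed 5% when the ORR in all treated patients is 5%. And the two tests can give opposite answers with no rule to choose between them, in an open-label study where replacement is optional.

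**Working it through.** **Inputs.** Null ORR 5%, one-sided exact binomial test at 0.05 (SAP 9.6.1; protocol 8.1.6). Planning ORR 20% with N=15 or 20 (protocol 3.6, Table 2). Cap of 30 dosed per cohort (protocol 3.6). The share *w* withdrawn in Cycle 1 is not in the documents; I take 10%, 20% and 30%, and assume that those withdrawn are all non-responders.

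**1. The plan's own figures.** The cut-off r is the smallest count with P(X ≥ r | n, 0.05) ≤ 0.05.
- n=15: P(X ≥ 2)=0.171 and P(X ≥ 3)=0.0362, so r=3. Power at 20% is P(X ≥ 3 | 15, 0.20)=0.602; Table 2 says 60%.
- n=20: P(X ≥ 3)=0.0755 and P(X ≥ 4)=0.0159, so r=4. Power is 0.589; Table 2 says 59%.

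All ten cells of Table 2 agree to within 0.5 percentage points. The cut-off is 3 for n=15–16, 4 for n=17–28 and 5 for n=29–40.

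**2. Evaluable set refilled to N.** If the ORR is 5% in all treated patients and a share w cannot respond, the ORR among Cycle 1 completers is q = 0.05/(1−w): 0.0556, 0.0625 and 0.0714. The false-positive rate for treated patients is P(X ≥ r | N, q).

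**3. Evaluable set without replacement.** N are dosed, the evaluable number m is Binomial(N, 1−w), and the cut-off r(m) is taken at m. The rate is the sum over m of P(m) × P(X ≥ r(m) | m, q).

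| N | w | q | Not replaced | Refilled to N |
|---|---|---|---|---|
| 15 | 10% | 0.0556 | 3.6% | 4.7% |
| 15 | 20% | 0.0625 | 3.6% | 6.3% |
| 15 | 30% | 0.0714 | 4.0% | 8.7% |
| 20 | 10% | 0.0556 | 2.2% | 2.3% |
| 20 | 20% | 0.0625 | 4.5% | 3.3% |
| 20 | 30% | 0.0714 | 6.6% | 5.0% |
| 30 | 10% | 0.0556 | 5.1% | 2.4% |
| 30 | 20% | 0.0625 | 6.0% | 3.7% |
| 30 | 30% | 0.0714 | 6.4% | 5.9% |

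A refilled evaluable set of 30 needs more than 30 dosed, so that column at N=30 is reachable only if replaced patients are left out of the cap.

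**4. FAS with replaced patients kept.** Replace until N complete Cycle 1, keep everyone in the denominator, and take the cut-off at the number dosed. For w=10%, 20% and 30% the false-positive rate is 2.8%, 1.9%, 2.0% at N=15; 2.3%, 3.1%, 3.2% at N=20; and 2.4%, 3.2%, 3.0% at N=30. It is always below 5%.

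**5. Disagreement between the sets.** Take 15 evaluable, 2 replaced (so 17 dosed) and 3 responders.
- Evaluable: P(X ≥ 3 | 15, 0.05) = 1 − (0.46329 + 0.36576 + 0.13475) = 0.0362, significant.
- FAS: P(X ≥ 3 | 17, 0.05) = 1 − (0.41812 + 0.37411 + 0.15752) = 0.0503, not significant; the cut-off at 17 is 4.

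The observed rates are 3/15 = 20.0% and 3/17 = 17.6%, so they also fall on opposite sides of the 20% observed-ORR benchmark in protocol 3.6.

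**The case against.** The strongest reply is that the plan already contains the right analysis. The FAS keeps every dosed patient, SAP 9.6.1 counts the unassessed as non-responders, and step 4 shows that this test stays below 5%. That stands. A reader might infer that replaced patients disappear from the primary ORR, or that the FAS test is inflated; the documents support neither. The higher cut-off at 17 dosed is conservative.

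Next, the selection comes from the definition of the evaluable set, which excludes early failures whether or not anyone is replaced. This stands in large part. At 20% and 30% withdrawal, replacement lowers the evaluable-set rate at N=20 and N=30; only N=15, of the sizes the plan names, shows a clear rise. The split in step 5 would also occur in a cohort that simply dosed 17 with 2 not evaluable.

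Other stronger readings fail too:
- **Loss of power.** FAS power falls from 49.8% (3 of 13 tolerating patients needed) to 35.2% (4 of 15) when 2 are replaced on a base of 15, taking a 20% ORR in patients who tolerate treatment. But over bases 15 to 30 with 1 or 2 replaced, FAS power rises in 26 of 32 cases.
- **Breach of the cap.** Section 3.6 caps patients administered drug, and nothing in section 5.3.2 overrides it.
- **Replacement of early progressors and deaths.** In section 5.3.2, disease progression is named only for Phase I. The PD clause could reach such patients, because target engagement needs a full cycle, but that is an inference: the clause is discretionary, and hematology PD needs only one dose.

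The withdrawal rates are also unsupported. Section 1.3 reports DLTs at 75 mg and 50 mg and mentions none at 25 mg BID. Section 3.3.2 allows up to 21 days for recovery, so withdrawals for non-recovery would tend to fall after Cycle 1.

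**Conclusion.** The point holds in a limited form. The plan runs the primary test at 0.05 in two sets, names neither as decisive, and does not say how replaced patients count. The evaluable-set test does not hold 5% for treated patients in general. Refilled, it ranges from 4.7% to 8.7% at N=15, 2.3% to 5.0% at N=20 and 2.4% to 5.9% at N=30, for assumed Cycle 1 withdrawal of 10% to 30%. Replacement is the main driver only at N=15; elsewhere the set definition is. The FAS test is sound.

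The sizes rest on the assumed rates, on withdrawn patients never responding, and on Cycle 1 withdrawal being the only reason to leave the evaluable set. The lack of a deciding set and the p=0.036 against p=0.0503 example need no withdrawal rate.

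**What to change.** In SAP section 9.6.1, name the FAS as the deciding analysis for the primary ORR test, with the cut-off taken at the realised number dosed (3 for 15–16, 4 for 17–28, 5 for 29–30), and report the Efficacy Evaluable set as supportive only.

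In protocol section 5.3.2, state that every dosed Phase II patient, including any who is replaced, counts toward the cohort N and the cap of 30 and stays in the ORR denominator; a replaced patient without a response counts as a non-responder. Limit PK, PD and biomarker replacement to reasons unrelated to outcome, such as a lost or unusable sample. The toxicity-replacement sentence need not be deleted: once all dosed patients count and the FAS decides, it no longer biases the primary result.

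The cost is a few sentences, a slightly less favourable headline ORR, and possibly fewer patients with complete PK or PD data.
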